6.1 Round 1 Control

The control round consists of 8 virtual patient cases (clinical vignettes). The 3 questionnaires (A/B/C) will consist of 6 clinical vignettes with the same risk profile as in the intervention round with a different description and in a different order.

The following baseline and self-assessment questions will be asked:

- Location of practice
- Type of practice
- Number of MDs associated with the practice
- Years of practice
- Proportion of patients covered by Medicare/Commercial insurance (<50% Medicare/>50% commercial; 50/50; >50% Medicare/<50% commercial)
- Estimate of number of GERD patients seen per week (<10; 10-20; ≥20)
- Rate your knowledge of Barrett's Esophagus (BE), esophageal adenocarcinoma (EAC), and associated risk factors (1 = not knowledgeable at all; 2 = not very knowledgeable; 3 = somewhat knowledgeable; 4 = very knowledgeable; 5 = expert)
- Rate your knowledge of the options and indications for BE screening (1 = not knowledgeable at all; 2 = not very knowledgeable; 3 = somewhat knowledgeable; 4 = very knowledgeable; 5 = expert)
- Rate the frequency in which you refer your GERD patients for endoscopic BE screening, as part of your standard practice (<20%; 20-40%; 40-60%; 60-80%; ≥80%)

The following questions will be asked per clinical vignette:

1. What level of risk for BE (and/or EC) do you think this patient has?
 - Low
 - Intermediate
 - High
2. Do you refer this patient for upper endoscopy?
 - Yes, I would refer this patient for endoscopy
 - No, I would not refer this patient for endoscopy

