6.2 Round 2 Intervention

The intervention round consists of 8 EsoGuard patient cases (clinical vignettes) (3 positive and 5 negative for EsoGuard). The 3 questionnaires (A/B/C) will have the same 5 negative EsoGuard cases, and 1 (different) positive EsoGuard case per questionnaire.

The following questions will be asked per clinical vignette:

1. What level of risk for BE (and/or EC) do you think this patient has?
 - Low
 - Intermediate
 - High
2. Do you refer this patient for upper endoscopy?
 - Yes, I would refer this patient for endoscopy
 - No, I would not refer this patient for endoscopy
3. Did the EsoGuard result influence your decision to refer or not refer the patient for upper endoscopy?
 - Yes; the EsoGuard result had an impact on my decision
 - No; the EsoGuard result had no impact on my decision

The following self-assessment questions will be asked of each participant at the end of round two (scale 1 very low to 5 high):

- Rate your understanding of EsoCheck/EsoGuard and its indications?
- How likely are you to use EsoCheck/EsoGuard for BE screening in your own practice?
- How likely are you to refer this technology to others or use in their practices?

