7.3 Statistical formulation and statistical analysis plan of the objectives

Primary objective: To determine the impact of EsoCheck/EsoGuard on health care provider's decision for upper endoscopy referral.

The impact will be measured by assessing the change in the percentage/rate of virtual patient cases who will be referred for endoscopy in the intervention round compared to the control round.

Statistics summarizing the agreement between the EsoGuard result (positive or negative) and the health care provider's decision (referral or no referral deemed necessary) include:

- positive agreement; percentage of EsoGuard positive virtual patient cases that were referred for endoscopy
- negative agreement; percentage of EsoGuard negative virtual patient cases that were not referred for endoscopy
- positive predictive value (PPV); percentage of referred virtual patient cases that are EsoGuard positive
- negative predictive value (NPV); percentage of non-referred virtual patient cases that are EsoGuard negative
- percentage of concordance

The participant-reported impact of EsoGuard results on their clinical decision making will be measured by assessing the proportion of patient cases in round 2 for which the provider answered the question, *“Did the EsoGuard result influence your decision to refer or not refer the patient for upper endoscopy”*, with, *“Yes; the EsoGuard result had an impact on my decision”* divided by all patient cases in round 2.

The provided answers will also be reported in a table with counts and percentages.

Secondary objective: To determine the impact of EsoCheck/EsoGuard on health care provider's patient risk assessment for BE.

The impact will be measured by assessing the change in the provider's virtual patient risk assessment for BE in the intervention round compared to the control round.

The provided answers will be reported in a table with counts and percentages.

The baseline and self-assessment questions, Round 1 Control, and Round 2 Intervention, will be reported in a table with counts and percentages.

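### The secondary analysis names only a table of counts and percentages for a change in a three-level risk rating, with no split by EsoGuard result and no paired shift analysis, so opposite shifts can be masked

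*Combined protocol and SAP*

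**What the plan says.** Under the secondary objective, section 7.3 takes as its measure the change in the provider's "virtual patient risk assessment for BE in the intervention round compared to the control round". The next sentence gives the output: "The provided answers will be reported in a table with counts and percentages". A general sentence at the end of the section adds: "The baseline and self-assessment questions, Round 1 Control, and Round 2 Intervention, will be reported in a table with counts and percentages". Nothing else in the section bears on the risk rating.

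The rating comes from one question, asked for every vignette in both rounds: "What level of risk for BE (and/or EC) do you think this patient has". The answers are Low, Intermediate and High.

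Two features of the design matter here. Section 6.2 fixes the case mix: "The 3 questionnaires (A/B/C) will have the same 5 negative EsoGuard cases, and 1 (different) positive EsoGuard case per questionnaire". Section 6.1 says that the Round 1 questionnaires contain "6 clinical vignettes with the same risk profile as in the intervention round with a different description and in a different order".

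For the primary objective, section 7.3 does plan summaries by test result. It introduces them as "Statistics summarizing the agreement between the EsoGuard result (positive or negative) and the health care provider's decision" and lists positive and negative agreement, PPV, NPV and concordance. All of these concern referral. There is no counterpart for the risk rating.

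**The concern.** The plan does not say what change means for a three-level ordered rating. It could be the difference in the percentage rated High, the share of ratings that move up or down, or a shift in the whole distribution. An analyst who compares the Low/Intermediate/High percentages of Round 1 with those of Round 2 over all cases would comply with section 7.3.

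That comparison has two weaknesses. First, it adds movements that should go in opposite directions, weighted five to one by the chosen case mix. The answer then depends on how many positive and negative vignettes were written as well as on how physicians respond to a result. Second, two marginal distributions do not show how many ratings rose, fell or stayed the same, although the same physicians rate matched risk profiles in both rounds.

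At stake is the answer to the secondary objective in a study meant to supply clinical utility data for reimbursement. A pooled table could show little or no change when both groups moved, or a net fall that hides a rise on positives. Because the summary is left open, it could also be chosen after the data are seen.

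**Working it through.** There is no planned figure to reproduce. Section 7.2 gives a minimum of 100 physicians completing both rounds, without alpha, power or effect size. The check is therefore on what a pooled table can show.

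**Inputs from the documents**
- Physicians completing both rounds: 100 (section 7.2).
- Cases per physician per round: 6. In Round 2, 5 are EsoGuard-negative and 1 is positive (section 6.2).
- Ratings per round: 100 × 6 = 600, of which 100 are on positives and 500 on negatives. Positives make up 100/600 = 16.7%.

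**Assumed inputs (not in the documents)**
- u: net share of positive-case ratings moving into High; range 40% to 100%.
- d: net share of negative-case ratings moving out of High; range 5% to 60%.

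**Pooled change in percentage High**

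Change = (100u − 500d)/600.

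- Largest contribution from positives (u = 100%): 100/600 = 16.7 points.
- Full cancellation: 100u = 500d, so d = u/5. The pairs (u, d) are (100%, 20%), (80%, 16%), (60%, 12%) and (40%, 8%).
- Dilution when d is smaller: u = 80%, d = 5% gives (80 − 25)/600 = +9.2 points for an 80-point rise on positives.
- Masking when d is larger: u = 80%, d = 40% gives (80 − 200)/600 = −20.0 points. The rise on positives is hidden inside a net fall, while the two net shifts together amount to (80 + 200)/600 = 46.7% of ratings.

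**Example in percentages.** Assume 40% High in Round 1 in both groups, then 30% of negatives and 90% of positives in Round 2. Pooled Round 2 = (5 × 30% + 90%)/6 = 40%. The pooled change is 0, with shifts of −10 and +50 points.

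**Example with all three levels (assumed counts, Low/Intermediate/High)**

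| Group | Round 1 | Round 2 | Change in High |
|---|---|---|---|
| Positive (100) | 20/60/20 | 0/20/80 | +60 points |
| Negative (500) | 100/300/100 | 120/340/40 | −12 points |
| Pooled (600) | 120/360/120 | 120/360/120 | 0 |

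A table split by result but still marginal leaves the second weakness in place. Among the negatives above, the fall from 100 to 40 High could be 60 ratings leaving and none entering, or 80 leaving and 20 entering. Only a Round 1 by Round 2 table separates these.

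**Precision after splitting and pairing.** The worst-case 95% half-width for the share that moved (p = 0.5) is as follows.
- Positives, 100 pairs, one per physician: 1.96 × √(0.25/100) = 9.8 points.
- Negatives, 500 pairs, five per physician, design effect 1 + 4 × ICC: 1.96 × √(0.25 × (1 + 4 × ICC)/500). This gives 4.4 points at ICC 0, and 5.2, 6.5 and 7.6 points at assumed ICCs of 0.1, 0.3 and 0.5.

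At the planned minimum size, both groups can be described separately with usable precision.

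**The case against.** The strongest reply is that section 7.3 does not forbid the right analysis. The sentence on the secondary objective fixes no layout, and a shift table split by EsoGuard result is itself a table of counts and percentages. The rounds are named only in the general closing sentence. A reader might infer that within-physician change is never measured, or that results will appear only as separate percentages per round. The text supports neither: it says that change in the provider's assessment will be assessed and leaves the method open. What remains is that the plan permits a shift analysis by result without requiring it.

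A second reply is that exact cancellation is a special case, and this is correct. Keep the 40% starting value and 90% High on positives, and put negatives at 20% High: the pooled figure is (5 × 20 + 90)/6 = 31.7%, a visible fall of 8.3 points. Put negatives at 10% and it is 23.3%, a fall of 16.7 points. The general risk is dilution or masking of the positive-case effect. In both of these cases the table shows a fall and gives no sign that positives rose by 50 points.

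A third reply is that pairing is partly inferred. The vignettes share risk profiles but differ in description and order. No matching key is given, and the documents do not say explicitly that a physician keeps the same letter in both rounds. This stands, and it limits what can be done within physician, above all for the single positive case, which differs by questionnaire.

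Finally, the objectives are descriptive and there is no decision rule, so no formal finding of no impact could follow. That also stands. It is also why no gain in standard error is claimed for pairing: the plan has no unpaired test or interval to compare with.

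**Conclusion.** The point holds as a gap in specification that affects how the secondary objective is answered. Change in the three-level rating is undefined, no split by EsoGuard result is planned for it, and no paired analysis is named. If the ratings are pooled, positives can move any percentage by at most 16.7 points. Their effect is diluted, and it disappears when the fall in negatives is one fifth of the rise in positives.

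The 16.7 points and the one-fifth condition follow from the 5:1 case mix in section 6.2 alone. The sizes of the shifts in the examples are assumptions, as is the expectation that ratings rise on positives and fall on negatives. It would go too far to conclude that the study cannot measure the change or that the plan will necessarily report no effect. Ratings are collected per vignette, so the split remains possible. The point is that it should be fixed in advance.

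**What to change.** In section 7.3, under the secondary objective:

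1. Define change as movement between the Round 1 and Round 2 ratings of vignettes with the same risk profile by the same physician.
2. Report 3 × 3 shift tables (Round 1 by Round 2), separately for EsoGuard-positive and EsoGuard-negative cases, with the percentages moving up, unchanged and down.
3. Give 95% intervals that allow for clustering by physician. This matters for the negatives, with five ratings per physician.
4. State the key that links each Round 1 vignette to its Round 2 counterpart. Round 1 cases carry no EsoGuard result, so they can be assigned to the positive or negative table only through this key.
5. State that each physician keeps the same questionnaire letter in both rounds. If the letter is not kept, compare the positive cases by risk profile rather than within physician.

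An ordinal model with round, EsoGuard result and their interaction, allowing for clustering by physician, is optional. The split shift tables already meet the concern.

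The cost is a few lines of SAP text, the documented key and a small amount of programming on data already to be collected. No participants or questions are added. The downside is two results in place of one pooled figure.

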8. ETHICAL CONSIDERATIONS

All participants must be appropriately informed about the participation in this study and sign an IRB approved consent form. Data will be collected for this research project in accordance with applicable laws and guidelines.

The protocol has been written and the study will be conducted according to the ICH Harmonized Tripartite Guideline for Good Clinical Practice.

